4.3.2.7 Assessment of Compliance

To assess patient compliance with self-administration of cobimetinib in Cohort 1 and cobimetinib and vemurafenib in Cohort 2, patients will be required to record the time and date they took each dose in a medication diary; missed doses will also be recorded. Patients will be instructed to bring all unused study medication and their medication diaries at specified study visits (see [Appendix 1](#) [Cohort 1] and [Appendix 2](#) [Cohort 2]) for assessments of compliance.

4.3.3 Investigational Medicinal Product Accountability

All IMPs required for completion of this study (cobimetinib and atezolizumab in Cohort 1 and cobimetinib, atezolizumab and vemurafenib in Cohort 2) will be provided by the Sponsor where required by local health authority regulations. *The study site should follow all instructions included with each shipment of IMP. The study site will acknowledge receipt of IMPs supplied by the Sponsor, by returning the appropriate documentation to confirm the shipment condition and content. Any damaged shipments will be replaced. The investigator or designee must confirm that appropriate temperature conditions have been maintained during transit, either by time monitoring (shipment arrival date and time) or temperature monitoring, for all IMPs received and that any discrepancies have been reported and resolved before use of the IMPs. All IMPs must be stored in a secure, environmentally controlled, and monitored (manual or automated) area in accordance with the labeled storage conditions, with access limited to the investigator and authorized staff.*

The IMPs will either be disposed of at the study site according to the study site's institutional standard operating procedure or be returned to the Sponsor (if supplied by the Sponsor) with the appropriate documentation. The site's method of destroying Sponsor-supplied IMPs must be agreed to by the Sponsor. The site must obtain written authorization from the Sponsor before any Sponsor-supplied IMP is destroyed, and IMP destruction must be documented on the appropriate form.

Accurate records of all IMPs received at, dispensed from, returned to, and disposed of by the study site should be recorded on the Drug Inventory Log.

4.3.4 Continued Access to Cobimetinib, Atezolizumab and Vemurafenib

The Sponsor will offer continued access to Roche IMPs cobimetinib, atezolizumab and vemurafenib free of charge to eligible patients in accordance with the Roche Global Policy on Continued Access to Investigational Medicinal Product, as outlined below.

A patient will be eligible to receive Roche IMPs atezolizumab and cobimetinib (Cohort 1 and Cohort 2 patients) and vemurafenib (Cohort 2 patients only) after completing the study if all of the following conditions are met:

- The patient has a life-threatening or severe medical condition and requires continued Roche IMP treatment for his or her well-being

Cobimetinib, atezolizumab, vemurafenib — F. Hoffmann-La Roche Ltd

66 / Protocol MO39136, Version 5.0

- There are no appropriate alternative treatments available to the patient
- The patient and his or her doctor comply with and satisfy any legal or regulatory requirements that apply to them

A patient will not be eligible to receive Roche IMPs cobimetinib and atezolizumab (Cohort 1 and Cohort 2 patients) and vemurafenib (Cohort 2 patients only) after completing the study if any of the following conditions are met:

- The Roche IMP is commercially marketed in the patient's country and is reasonably accessible to the patient (e.g., is covered by the patient's insurance or wouldn't otherwise create a financial hardship for the patient)
- The Sponsor has discontinued development of the IMP or data suggest that the IMP is not effective for metastatic melanoma
- The Sponsor has reasonable safety concerns regarding the IMP as treatment for metastatic melanoma
- Provision of the Roche IMP is not permitted under the laws and regulations of the patient's country

The Roche Global Policy on Continued Access to Investigational Medicinal Product is available at the following Web site:

http://www.roche.com/policy_continued_access_to_investigational_medicines.pdf

4.4 CONCOMITANT THERAPY

Concomitant therapy consists of any medication (e.g., prescription drugs, over-the-counter drugs, vaccines, herbal or homeopathic remedies, nutritional supplements) used by a patient in addition to protocol-mandated treatment from seven days prior to initiation of study treatment until 28 days after the last dose of study treatment. All such medications should be reported to the investigator and recorded on the Concomitant Medications electronic Case Report Form (eCRF).

4.4.1 Permitted Therapy

Patients who use oral contraceptives, hormone-replacement therapy, prophylactic anticoagulation therapy (such as low-molecular-weight heparin at a stable dose level), or other allowed maintenance therapy should continue their use. Male and female patients of reproductive potential should use highly effective means of contraception (see Section 4.1.1).

Patients are permitted to use the following therapies during the study:

- Oral contraceptives with a failure rate of <1% per year (see Section 4.1.1)
- Hormone-replacement therapy
- Prophylactic or therapeutic anticoagulation therapy such as low-molecular-weight heparin. Note that coumarin anticoagulants are not permitted during the study.

- Vaccinations (such as influenza, COVID-19); however, live, attenuated vaccines are not permitted (see Section 4.4.5)
- Megestrol acetate administered as an appetite stimulant
- Inhaled corticosteroids administered for COPD or asthma
- Mineralocorticoids (e.g., fludrocortisone)
- Low-dose corticosteroids administered for orthostatic hypotension or adrenocortical insufficiency
- Pain medications as indicated, as per standard practice

In general, investigators should manage a patient's care (including pre-existing conditions) with supportive therapies other than those defined as cautionary or prohibited therapies (see Sections 4.4.2 and 4.4.5) as clinically indicated, per local standard practice.

Anti-emetic medications, antidiarrheal medications and hematopoietic growth factors are not to be administered prophylactically prior to initiation of study treatment. However, at the discretion of the investigator, anti-emetic medications, antidiarrheal medications and hematopoietic growth factors may be administered prophylactically per standard local practice before the second and subsequent doses of study treatment. In addition, premedication with antihistamines, antipyretics, and/or analgesics may be administered for the second and subsequent atezolizumab infusions only, at the discretion of the investigator.

Patients who experience infusion-associated symptoms may be treated symptomatically with ibuprofen, diphenhydramine, and/or H2-receptor antagonists (e.g., famotidine, cimetidine), or equivalent medications per local standard practice (acetaminophen is prohibited for patients in Cohort 2 only - see Section 4.4.5). Serious infusion-associated events manifested by dyspnoea, hypotension, wheezing, bronchospasm, tachycardia, reduced oxygen saturation or respiratory distress should be managed with supportive therapies as clinically indicated (e.g., supplemental oxygen and β 2-adrenergic agonists; see Appendix 11).

4.4.2 Cautionary Therapy

4.4.2.1 Antiplatelet Agents

Antiplatelet agents should be used with caution during study treatment.

4.4.2.2 Systemic Corticosteroids, Immunosuppressive Medications, and TNF- α Inhibitors

Systemic corticosteroids, *immunosuppressive medications*, and TNF- α inhibitors may attenuate potential beneficial immunologic effects of treatment with atezolizumab. If feasible, alternatives to these agents should be considered.

Corticosteroids administered to control symptoms of cerebral oedema and mass effect must be reported in the eCRF. Dosage, frequency, dates of administration and route of administration must be recorded in the dedicated eCRF pages.

For treatment of vemurafenib-related adverse events in Cohort 2 (other than hepatotoxicity as outlined in Section 5.1.5.2), systemic corticosteroids may be administered at the lowest effective dose and for the shortest possible duration deemed necessary by the investigator.

Topical corticosteroids are allowed for suspected cutaneous autoimmune reactions. Megestrol may be administered as an appetite stimulant during the study. In situations in which systemic corticosteroids, *immunosuppressive medications*, or TNF- α inhibitors would be routinely administered, alternatives, including antihistamines, should be considered. If the alternatives are not feasible, systemic corticosteroids, *immunosuppressive medications*, and TNF- α inhibitors may be administered at the discretion of the investigator.

Systemic corticosteroids or *immunosuppressive medications* are recommended, at the discretion of the investigator, for the treatment of specific adverse events when associated with atezolizumab therapy (refer to the Atezolizumab Investigator's Brochure for details).

4.4.2.3 Bisphosphonates

Patients who are receiving bisphosphonates to enrollment should be maintained on bisphosphonate during study treatment. Initiation of bisphosphonates is discouraged during study treatment because of their potential immunomodulatory properties. However, initiation of such treatment should not result in study treatment discontinuation.

4.4.2.4 Medications Given with Precaution due to Effects Related to Cytochrome P450 Enzymes

Cautionary therapies applicable to patients receiving cobimetinib (Cohorts 1 and 2):

- Concomitant use of strong and moderate inhibitors of CYP3A (e.g., clarithromycin, itraconazole, ketoconazole, posaconazole, telithromycin, and voriconazole) should be avoided during cobimetinib treatment because cobimetinib is a sensitive substrate of CYP3A and exposures will be increased in presence of these agents (approximately 7-fold increase in presence of itraconazole in healthy subjects).
- Strong and moderate CYP3A inducers (e.g., rifampin, phenytoin, carbamazepine, and phenobarbital) should be avoided during cobimetinib treatment because they increase the metabolism of cobimetinib. Strong inducers of CYP3A4 should be avoided, or selection of an alternate concomitant medicinal product with no or minimal potential to induce CYP3A4 should be considered.

Cautionary therapies applicable to patients receiving vemurafenib (Cohort 2 only):

- Vemurafenib is a moderate CYP1A2 inhibitor and a CYP3A4 inducer. Concomitant use of vemurafenib with agents with a narrow therapeutic window that are metabolized by CYP1A2 and CYP3A4 is not recommended. If co-administration cannot be avoided, exercise caution, as vemurafenib may increase plasma exposure of CYP1A2 substrate drugs and decrease plasma exposure of CYP3A4 substrate drugs. Dose reduction of the concomitant CYP1A2 substrate drug may be considered, if clinically indicated. Acetaminophen is a CYP1A2 substrate and is prohibited for patients in Cohort 2 (see Section 4.4.5).
- In two drug-drug interaction studies, vemurafenib increased the exposure of a single, oral dose of digoxin. An approximate 1.8- and 1.5-fold increase in digoxin area under the concentration-time curve (AUC) from Time 0 to the last measurable concentration and maximum concentration, respectively, was observed in a prior study (Study GO28394). Digoxin and other p-glycoprotein substrates with a narrow therapeutic window are prohibited within seven days prior to initiation of vemurafenib, during vemurafenib treatment, and for 28 days after the last dose of vemurafenib.
- *In vitro* data have demonstrated that vemurafenib is a moderate inhibitor of CYP2C8. CYP2C8 substrates with a narrow therapeutic window should be used with caution, as their concentration may be increased when co-administered with vemurafenib.
- *In vitro* data have demonstrated that vemurafenib is a substrate of CYP3A4. Thus, strong CYP3A4 inhibitors (e.g., ketoconazole, itraconazole, clarithromycin, atazanavir, nefazodone, saquinavir, telithromycin, ritonavir, indinavir, nelfinavir, voriconazole) and inducers (e.g., phenytoin, carbamazepine, rifampin, rifabutin, rifapentine, phenobarbital) should be used with caution when co-administered with vemurafenib.

The above lists of medications are not necessarily comprehensive. The investigator should consult the prescribing information when determining whether a concomitant medication can be safely administered with study treatment. In addition, the Medical Monitor *is available to advise* if questions arise regarding medications not listed above.

4.4.2.5 Herbal Therapies

Concomitant use of herbal therapies is not recommended because their pharmacokinetics, safety profiles, and potential drug-drug interactions are generally unknown. However, herbal therapies not intended for the treatment of cancer may be used during the study at the discretion of the investigator.

4.4.2.6 Medications Affecting the QT Interval – Cohort 2 Only

Caution should be exercised when Cohort 2 study treatment is co-administered with drugs that cause QT prolongation or cardiac arrhythmia, especially in patients with a pre-existing cardiac disease or ECG abnormality that may predispose them to cardiac dysrhythmia. Investigators should closely monitor patients who are on medications or

supplements that may affect the QT interval. Alternative treatment options for medications known to affect QT interval should be discussed with each patient prior to their enrollment in this study. Additional information is available at the following Internet site:

<https://crediblemeds.org/healthcare-providers/>

The effect of vemurafenib 960 mg BID on QT interval was evaluated in a multicentre, open-label, single-arm study in 132 previously-treated patients with BRAF^{V600} mutation-positive metastatic melanoma (Study NP22657). No large changes from baseline in mean QTc interval (i.e., > 20 ms) were detected in the study. However, vemurafenib is associated with concentration-dependent QT prolongation.

Although nonclinical studies showed a low potential for QT-interval prolongation with cobimetinib, no additive effect on QT-interval prolongation was observed when patients were treated with cobimetinib in combination with vemurafenib in Study GO28141. A combined cobimetinib and vemurafenib concentration-QTcF model (for which 433 patients contributed 1031 cobimetinib and vemurafenib observations) provided no evidence that cobimetinib prolonged QTcF interval when co-administered with vemurafenib.

4.4.3 Stereotactic Radiation in Cohort 2

Stereotactic radiation is permissible as described in Section 4.3.2.3. Due to vemurafenib radiation recall and radiation sensitization (see Section 5.1.3.10), caution should be used when giving vemurafenib concomitantly or sequentially with radiation treatment.

4.4.4 Cautionary Food

Due to a possible increased risk of liver toxicity, the consumption of alcohol during study treatment is not recommended.

4.4.5 Prohibited Therapy

Use of the following concomitant therapies is prohibited as described below:

- Other than SRT as described in Section 4.3.2.3, concomitant therapy intended for the treatment of cancer (including, but not limited to, chemotherapy, hormonal therapy, immunotherapy, radiotherapy for palliative or other purposes, and herbal therapy), whether health authority-approved or experimental, is prohibited for various time periods prior to starting study treatment, depending on the agent (see Section 4.1.2), and during study treatment.
- Investigational therapy is prohibited within 28 days (or 5 half-lives of the drug, whichever is longer), prior to initiation of study treatment and during study treatment.
- Anti-emetic medications, antidiarrheal medications and hematopoietic growth factors are not to be administered prophylactically prior to initiation of study treatment.

- Anti-arrhythmic agents and medications with a risk of torsades de pointes are prohibited within seven days prior to initiation of study treatment, during study treatment, and for 28 days after the last dose of study treatment.
- Denosumab (a RANKL inhibitor) is prohibited during atezolizumab treatment because it could potentially alter the efficacy and safety of atezolizumab. Patients who are receiving denosumab prior to enrollment must be willing and eligible to receive a bisphosphonate instead while in the study.
- Live, attenuated vaccines (e.g., FluMist®) are prohibited within four weeks prior to initiation of study treatment, during atezolizumab treatment, and for 5 months after the last dose of atezolizumab.
- Systemic immunostimulatory agents (including, but not limited to, interferons and IL-2) are prohibited within 28 days or 5 half-lives of the drug (whichever is longer) prior to initiation of study treatment and during study treatment because these agents could potentially increase the risk for autoimmune conditions when given in combination with atezolizumab.
- St. John's wort is prohibited during study treatment and for two weeks after the last dose of cobimetinib or vemurafenib (whichever is later)
- Coumarin anticoagulants are prohibited during study treatment
- *For patients in Cohort 2 only*, acetaminophen is prohibited within seven days prior to initiation of study treatment, during study treatment, and for 28 days after the last dose of study treatment, unless the patient has an absolute contraindication to the use of NSAIDs or aspirin (i.e., severe allergy or reactive airway disease sensitive to NSAIDs or aspirin). See Section 4.4.2.4.

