4.3 STUDY TREATMENT

Cobimetinib and atezolizumab are the investigational medicinal products (IMPs) in Cohort 1 and cobimetinib, atezolizumab and vemurafenib are the IMPs in Cohort 2.

In this protocol, "study treatment" refers to the combination of treatments assigned to patients as part of this study (i.e. atezolizumab and cobimetinib in Cohort 1, and cobimetinib, atezolizumab and vemurafenib in Cohort 2).

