5.1.6 Management of Patients Who Experience Specific Adverse Events

5.1.6.1 Dose Modifications – Cohort 1

General dose modification guidelines for cobimetinib are provided in [Table 5](#). Dose modification guidelines for specific adverse events with combination treatment in this cohort are provided in [Appendix 12](#). Additional guidelines for the management of adverse events associated with atezolizumab are provided in [Appendix 14](#). After dose reduction, consideration may be given to allow for dose escalation of cobimetinib by a maximum of one dose level (20 mg) increments following resolution of the adverse event that resulted in dose modification to \leq Grade 1 and provided there are no safety concerns.

There will be no dose modifications for atezolizumab in this study.

Table 5 Recommended Cobimetinib Dose Modifications

Grade (NCI CTCAE)	Recommended Cobimetinib Dose
Grade 1 or Grade 2 (tolerable)	No dose reduction. Maintain cobimetinib at the same dose of 60 mg QD (3 tablets).
Grade 2 (intolerable) or Grade 3 or 4 (any)	
First appearance:	Interrupt treatment until Grade \leq 1: restart treatment at 40 mg QD (2 tablets).
Second appearance:	Interrupt treatment until Grade \leq 1: restart treatment at 20 mg QD (1 tablet).
Third appearance:	Consider permanent discontinuation.

NCI CTCAE = National Cancer Institute Common Terminology Criteria for Adverse Events;
QD = once a day.

5.1.6.2 Dose Modifications – Cohort 2

Run-in period (Cycle 1)

During the run-in period (Cycle 1, Days 1-28), one dose level reduction of cobimetinib and vemurafenib is permitted for management of drug-related toxicities. No further dose reductions are permitted in the run-in period. If toxicities do not improve within 28 days following the one level dose reduction and/or treatment interruption for either cobimetinib and/or vemurafenib, study treatment should be discontinued, unless *the patient is likely to derive clinical benefit. The decision to re-challenge patients with study treatment should be based on investigator's assessment of benefit–risk and documented by the investigator (or an appropriate delegate). The Medical Monitor is available to advise as needed.* The run-in period may be extended to a total of 56 days to allow patients to recover from drug-related toxicities prior to proceeding to Cycle 2. Following a dose reduction in the run-in period (Cycle 1), no escalation is permitted.

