In general, toxicities should be managed with supportive care, dose modifications (as permitted), and treatment interruptions applied to the component of the study treatment judged to be the primary cause. Additional tests or procedures, such as autoimmune serology or biopsies to obtain tissue samples, may be performed to determine a possible immunogenic aetiology. This also applies to cases where the severity exceeds previously observed toxicities, or nature of the toxicity encountered differs from the known safety profile. Special attention to cases of severe cutaneous hypersensitivity reactions, such as Drug Rash with Eosinophilia and Systemic Symptoms (DRESS) is warranted from study investigators.

For management of cobimetinib- and atezolizumab-specific toxicities, including IRRs, gastrointestinal toxicity, dermatologic toxicity, hepatotoxicity, pulmonary toxicity, potential eye toxicity, reductions in LVEF from baseline, rhabdomyolysis, elevated CPK and haemorrhage, see [Appendix 12](#). Additional guidelines for the management of adverse events associated with atezolizumab are provided in [Appendix 14](#) .

5.1.6.5 Management Guidelines – Cohort 2

In general, toxicities should be managed with supportive care, dose modifications (as permitted), and treatment interruptions applied to the component of the study treatment judged to be the primary cause. Additional tests or procedures, such as autoimmune serology or biopsies to obtain tissue samples, may be performed to determine a possible immunogenic aetiology.

Cohort 2 patients should be monitored closely upon initiation of atezolizumab as a third treatment component on Days 1 and 15 of Cycles 2 and 3, as well as the days immediately following these visits. Regular telephone contact and, if needed, unscheduled laboratory tests are strongly recommended.

Guidelines for management of patients who experience specific adverse events in this cohort are provided in [Appendix 13](#). The table also includes general guidelines for dose

modifications and treatment delays and discontinuation. Additional guidelines for the management of adverse events associated with atezolizumab are provided in [Appendix 14](#). The guidelines in [Appendix 13](#) and [Appendix 14](#) are not intended to replace clinical judgment or dictate care of individual patients.

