Immune-mediated myocarditis, Grade 2-4	
Permanently discontinue atezolizumab and contact Medical Monitor [a].Refer patient to cardiologist.Initiate treatment as per institutional guidelines and consider antiarrhythmic drugs, temporary pacemaker, ECMO, or VAD as appropriate.Initiate treatment with 1–2 mg/kg/day IV methylprednisolone or equivalent and convert to 1–2 mg/kg/day oral prednisone or equivalent upon improvement.If event does not improve within 48 hours after initiating corticosteroids, consider adding an immunosuppressive agent.If event resolves to Grade 1 or better, taper corticosteroids over \geq 1 month.

ECMO = extracorporeal membrane oxygenation; VAD = ventricular assist device.

a. Resumption of atezolizumab may be considered in patients who are deriving benefit and have fully recovered from the immune-mediated event. *The decision to re-challenge patients with atezolizumab should be based on investigator's assessment of benefit-risk and documented by the investigator (or an appropriate delegate). The Medical Monitor is available to advise as needed.*

INFUSION-RELATED REACTIONS AND CYTOKINE-RELEASE SYNDROME

No premedication is indicated for the administration of Cycle 1 of atezolizumab. However, patients who experience an IRR or CRS with atezolizumab may receive premedication with antihistamines, antipyretics and/or analgesics (acetaminophen is prohibited for patients in Cohort 2 only; see [Section 4.4.5](#)) for subsequent infusions. Metamizole (dipyrone) is prohibited in treating atezolizumab-associated IRRs because of its potential for causing agranulocytosis.

Appendix 14:Risks Associated with Atezolizumab and Guidelines for Management of Adverse Events Associated with Atezolizumab

IRRs are known to occur with the administration of monoclonal antibodies and have been reported with atezolizumab. These reactions, which are thought to be due to release of cytokines and/or other chemical mediators, occur within 24 hours of atezolizumab administration and are generally mild to moderate in severity.

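### Section 4.4.5 prohibits anti-arrhythmic agents that Appendix 14 tells sites to consider for immune-mediated myocarditis, and nothing in the protocol reconciles the two

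*Protocol*

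**What the plan says.** Protocol Section 4.4.5 (Prohibited Therapy) has one bullet on this drug class. It opens "Anti-arrhythmic agents and medications with a risk of torsades de pointes are prohibited within seven days prior to initiation of study treatment" and continues "during study treatment, and for 28 days after the last dose of study treatment". It names no cohort and contains no exception.

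Protocol Appendix 14, Table 6 covers immune-mediated myocarditis of Grade 2 to 4. Atezolizumab is stopped permanently, a cardiologist is involved, corticosteroids are started, and sites are told: "Initiate treatment as per institutional guidelines and consider antiarrhythmic drugs, temporary pacemaker, ECMO, or VAD as appropriate". The table does not restrict the choice of agent and does not mention Section 4.4.5.

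Sections 5.1.6.1 (Cohort 1) and 5.1.6.2 (Cohort 2) both send sites to Appendix 14. Section 4.3 says that study treatment "refers to the combination of treatments assigned to patients as part of this study", so the term means the whole regimen and not atezolizumab alone.

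**The concern.** The event is an anticipated one. Section 5.1.2 lists myocarditis among the atezolizumab risks. Section 5.2.3 makes cardiac disorders of Grade 2 or above adverse events of special interest, with atrial fibrillation and myocarditis among the examples. In such a case one part of the protocol bars a drug class that another part invites the site to consider.

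The sponsor has dealt with a conflict of this kind before. Immunosuppressive medications now sit under cautionary therapy in Section 4.4.2.2, and the amendment summary gives agreement with Appendix 14 as the reason. The anti-arrhythmic bullet has had no matching adjustment. That history is only a precedent; the inconsistency lies in the current text of Section 4.4.5 and Table 6.

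**Working it through.** No arithmetic beyond dates applies and the plan has no figure to reproduce, so the check is a comparison of the passages.

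1. **Drugs.** Section 4.4.5 can be read in two ways. If the torsades phrase attaches only to the second noun, every anti-arrhythmic agent is barred. If it attaches to both nouns, only torsades-risk anti-arrhythmics are barred. Table 6 places no limit on the agents to be considered, so the two passages overlap on either reading: on the whole class under the first, on a subset under the second.

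2. **Time.** The ban runs from 7 days before the first dose of study treatment to 28 days after the last. Table 6 becomes relevant once atezolizumab has been given. In Cohort 1 that is Cycle 1 Day 1. In Cohort 2 it is Cycle 2 Day 1, after a run-in of 28 days (Section 4.3.2.2), extendable to a total of 56 (Section 5.1.6.2). The overlap therefore runs from the first atezolizumab dose to 28 days after the last dose of study treatment. Serious events and events of special interest are collected for 90 days after the last dose, or until new systemic anti-cancer therapy if sooner (Section 5.3.1). A myocarditis first treated in the remaining 90 − 28 = 62 days is outside the ban.

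3. **Whether stopping drugs lifts the ban.** Stopping atezolizumab does not, because study treatment means the combination. For the other drugs, the catch-all rows in Appendix 12, Table 1 (Cohort 1) and Appendix 13, Table 13 (Cohort 2) withhold the entire regimen for treatment-related toxicities with no entry of their own, if these are Grade 3–4 or an intolerable Grade 2. Myocarditis has no entry of its own in either appendix, so these rows would apply. Even then, acute treatment can fall within 28 days of the last dose. Tolerable Grade 2 cases are not caught by those rows. If a Cohort 2 case is handled as a symptomatic fall in ejection fraction, Appendix 13, Table 12 withholds cobimetinib but continues atezolizumab and vemurafenib.

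4. **Whether an exception exists elsewhere.** None was found in the protocol or SAP.
   - Section 4.4.1 allows supportive care, but excludes the therapies listed as prohibited.
   - Section 5.1.6.5 says that the guidelines in Appendices 13 and 14 "are not intended to replace clinical judgment or dictate care of individual patients". That qualifies the appendices, not the prohibited list.
   - Section 4.4.5 does write exceptions where they are meant: one for stereotactic radiotherapy and one for acetaminophen. The anti-arrhythmic bullet has neither kind.
   - Section 9.2 does not allow prospective requests to deviate, so a site cannot clear the conflict in advance.

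5. **Analysis.** SAP Section 4 defines the Evaluable Population by receipt of study medication and at least two post-baseline intracranial assessments. Use of a prohibited medication does not enter that definition, so the primary response rate is not altered by how the conflict is resolved. SAP Section 5.7.1 summarises major protocol deviations, but the documents do not say whether this use would count as one.

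**The case against.** The strongest reply is that Table 6 is permissive. Antiarrhythmic drugs are one of four options to consider as appropriate, and a site that chooses none of the barred agents complies with both passages. That is correct, and it is why the point is an inconsistency and not a pair of opposite orders. It does not remove the problem: the table still offers, without a caveat, something the protocol prohibits.

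Several stronger readings are tempting, and the documents do not support them.

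- A reader might infer that vemurafenib keeps running in Cohort 2 because Appendix 14 stops only atezolizumab. Appendix 14 is a supplement. The Appendix 13 catch-all withholds every study drug in Grade 3–4 or intolerable Grade 2 events. What is left is tolerable Grade 2 and cases managed under the ejection-fraction table.
- A reader might infer that the conflict covers every Grade 2–4 myocarditis with arrhythmia from the first dose onward. Cohort 2 receives no atezolizumab in the run-in, and events treated later than 28 days after the last dose fall outside the ban. Nothing in Appendix 14 defines myocarditis as arising on or soon after treatment.
- A reader might infer that rescue would be delayed. Appendix 14 requires urgent evaluation, a cardiologist, corticosteroids and contact with the Medical Monitor, and Section 5.4.1 provides a round-the-clock emergency line. Nothing shows that a site would hold back acute care because of a concomitant-medication list.
- A reader might take it as settled that all anti-arrhythmics are banned. The grammar of the bullet leaves that open.

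**Conclusion.** The point holds within stated limits. For immune-mediated myocarditis of Grade 2–4 arising after atezolizumab has started and up to 28 days after the last dose of study treatment, using the Appendix 14 option breaches Section 4.4.5. On the narrower reading of the torsades phrase the breach is confined to torsades-risk anti-arrhythmics.

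This rests on two assumptions. The first is that study treatment carries its Section 4.3 meaning in Section 4.4.5. The second is that no exception exists in material outside the protocol and SAP.

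The documents give no rate for the event, so its frequency cannot be stated. There is no effect on the primary estimate. The importance is minor for the analysis; the reason to act is that sites need one consistent rule for a serious event the protocol itself anticipates. Which rule is clinically right is not judged here.

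**What to change.** Reconcile Section 4.4.5 with Appendix 14, Table 6. In Section 4.4.5, state whether anti-arrhythmic treatment of an adverse event is excepted from the prohibition, and state whether the torsades phrase qualifies anti-arrhythmic agents. Add a cross-reference in each direction between the two passages, and one to the Appendix 12 and 13 rules for the other study drugs, including the ejection-fraction rows that can overlap with myocarditis. The clinical team decides the content of the rule.

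The drafting amounts to a sentence or two plus the cross-references. Because it changes a protocol rule, it needs an amendment with ethics approval and, where locally required, regulatory approval (Section 9.7). It could travel with the next planned amendment. No change to the SAP, the sample size or any analysis is needed.
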